APPENDIX C: IW-CLL GRADING SCALE FOR HEMATOLOGIC TOXICITY IN CLL STUDIES

Grade#	Decrease in Platelets* or Hb° (nadir) from Baseline Value, %	Absolute neutrophil count/μL (nadir)§
0	No change to 10%	≥2000
1	11% - 24%	≥1500 and <2000
2	25% - 49%	≥1000 and <1500
3	50% - 74%	\geq 500 and <1000
4	≥75%	< 500

Grades: 1, mild; 2, moderate; 3 severe; 4 life-threatening; 5 fatal. Death occurring as a result of toxicity at any level of decrease from baseline will be recorded as grade 5.

- * Platelet counts must be below normal levels for grades 1-4. If, at any level of decrease the platelet count is $<20,000/\mu L$, this will be considered grade 4 toxicity, unless a severe or life-threatening decrease in the initial platelet count (e.g. $20,000/\mu L$) was present at baseline, in which case the patient is not evaluable for toxicity referable to platelet counts.
- ° Hb levels must be below normal levels for grades 1 to 4. Baseline and subsequent Hb determinations must be performed before any given transfusions. The use of erythropoietin is irrelevant for the grading of toxicity but should be documented.
- \S If the absolute neutrophil count (ANC) reaches $<1000/\mu L$, it should be judged to be grade 3 toxicity. Other decreases in the white blood cell count, or in circulating granulocytes, are not to be considered, since a decrease in the white blood cell count is a desired therapeutic endpoint. A gradual decrease in granulocytes is not a reliable index in CLL for stepwise grading of toxicity. If the ANC was $<1000/\mu L$ prior to therapy, the patient is not evaluable for toxicity referable to the ANC. The use of growth factors such as G-CSF is not relevant to the grading of toxicity, but should be documented

APPENDIX D: CAIRO-BISHOP DEFINITIONS OF LABORATORY AND CLINICAL TUMOR LYSIS SYNDROME (TLS)

Table 1. Cairo-Bishop Definition of Laboratory Tumor Lysis Syndrome[‡]

Element	Value	Change from Baseline
Uric Acid	\geq 476 μ mol/L or 8 mg/dL	25% increase
Potassium	\geq 6.0 mmol/L or 6 mg/L	25% increase
Inorganic Phosphorus	\geq 1.45 mmol/L or 5mg/dL	25% increase
Calcium	\leq 1.75 mmol/Lor 7mg/dL	25% decrease

Table 2. Cairo-Bishop Clinical Tumor Lysis Syndrome Definition and Grading † $_{\rm Grade}$

Complication	0	1	2	3	4	5
Creatinine*	≤1.5 × ULN	1.5 × ULN	1.5 – 3.0 × ULN	> 3.0 – 6.0 × ULN	> 6.0 × ULN	Death
Cardiac Arrhythmia*	None	Intervention not indicated	Non-urgent medical intervention indicated	Symptomatic and incompletely controlled medically or controlled with device (e.g., defibrillator)	Life-threatening (e.g., arrhythmia associated with CHF, hypotension, syncope, shock)	Death
Seizure*	None	_	One brief, generalized seizure; seizure(s) well controlled by anticonvulsants or infrequent focal motor seizures not interfering with ADL	Seizure in which consciousness is altered; poorly controlled seizure disorder; with breakthrough generalized seizures despite medical intervention	Seizure of any kind which are prolonged, repetitive or difficult to control (e.g., status epilepticus, intractable epilepsy)	Death

ULN = upper limit of normal; CHF = congestive heart failure; ADL = activities of daily living

Two or more values from Table 1 must have the prespecified change to meet criteria for laboratory TLS. Either the absolute value or the percent change for each element can count towards one criterion.

^{*} Not directly or probably attributable to the apeutic agent.

[†] Clinical tumor lysis syndrome is defined as laboratory tumor lysis syndrome and at least one clinical complication.

APPENDIX E: RECOMMENDATIONS FOR INITIAL MANAGEMENT OF ELECTROLYTE ABNORMALITIES AND PREVENTION OF TUMOR LYSIS SYNDROME

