5.2 Pre-Treatment Criteria

Cycle 1, Day 1

Participants must meet all of the inclusion criteria, have none of the exclusion criteria, and must be registered to the protocol prior to initiating therapy.

C1D1 laboratory results need not meet eligibility parameters again provided that they met criteria at screening and in the opinion of the treating investigator do not pose any undue risk to the participant.

Cycle 4 Days 1, 2, 8, 15, 22

These are the days of venetoclax initiation or dose escalation. Tumor lysis labs (potassium, uric acid, phosphorous, calcium, and creatinine) must be checked prior to the patient receiving their dose of venetoclax, and must not meet Cairo Bishop criteria (Appendix D) for TLS. If criteria for TLS are met, the venetoclax dose should be delayed until electrolytes return to baseline.

All cycles subsequent to cycle 1

If labs are checked prior to cycle initiation, then the following criteria must be met:

- ANC must be $> 500/\text{mm}^3$
- Platelet count must be $\geq 20k/\mu L$ (may be $10-20k/\mu L$ if transfusion support is also given)
- All non-hematologic toxicities must have resolved to ≤ Grade 2, or to the patient's baseline condition

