Venetoclax will be administered orally once daily and given in continuous 28-day cycles. Venetoclax administration will begin on cycle 4 day 1. If patients are in an MRD-negative CR/CRi at the end of cycle 15, then patients will have the option to discontinue venetoclax at this time. If patients are not in an MRD-negative CR/CRi at the end of cycle 15, then venetoclax will be continued (along with acalabrutinib) through cycle 24, at which point another response assessment will occur. If patients are not in an MRD-negative state at this time, venetoclax (with acalabrutinib) will continue indefinitely until progression or toxicity. If patients are in an MRD-negative state, they will have the option to discontinue venetoclax and the patient will be monitored for disease recurrence.

Venetoclax is initiated with a dose ramp-up to reduce the risk of tumor lysis syndrome. In this trial, we will use a slightly modified dose escalation strategy since the patients will have already had significant debulking of their disease with three prior cycles of acalabrutinib and two prior cycles of obinutuzumab. This dosing regimen of escalating from 20 mg to 50 mg on day 2 is modeled after the experience from the M13-982 venetoclax trial, which showed that this is a safe approach (Stilgenbauer et al., 2016). The dosing schedule for venetoclax in this trial is as follows. Note that this ramp-up schedule cannot be shortened, but may be lengthened if TLS is observed.

Day of treatment cycle	Venetoclax Daily Dose
Cycle 4, day 1	20mg
Cycle 4, days 2-7	50mg
Cycle 4, days 8-14	100mg
Cycle 4, days 15-21	200mg
Cycle 4, days 22-28	400mg
Cycles 5 and beyond	400mg

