- For patients at low or medium risk of tumor lysis syndrome (as defined in section 6.1.2), venetoclax will be given as a 20mg oral dose on cycle 4 day 1. Patients will receive intravenous hydration of 150-200ml/hr while in the outpatient infusion area. Tumor lysis labs (including potassium, uric acid, phosphorous, calcium, and creatinine) must be checked on cycle 4 day 1 prior to this dose, approximately 6-8 hours after dosing, and again the following day, approximately 24 hours after the initial dose (prior to the second dose of venetoclax on cycle 4 day 2). If Cairo-Bishop criteria (Appendix D) for laboratory or clinical tumor lysis syndrome (TLS) are met on these follow-up labs, TLS management will occur as per Appendix E, and the patient will either have drug held or continue at 20mg daily (depending on severity) until the changes resolve, at which point the patient will escalate to 50mg daily. If Cairo-Bishop criteria for TLS are not met, the patient will dose escalate to 50mg on day 2. TLS labs should be checked again on cycle 4 day 2 approximately 6-8 hours after dosing and approximately 24 hours post the first 50mg dose.
- Patients at high risk of TLS (as defined in section 6.1.2) will be admitted to the hospital for venetoclax initiation. Patients will receive intravenous hydration of 150-200ml/hr, prior to receiving their first dose of venetoclax 20mg. Tumor lysis labs will be checked on cycle 4 day 1 prior to this initial dose and then at approximately 4, 8, 12, and 24 hours later. If Cairo-Bishop criteria for tumor lysis syndrome are not met (see Appendix D), the patient will be escalated to 50mg daily on cycle 4 day 2. Tumor lysis labs will then be checked approximately 4, 8, 12, and 24 hours after this second dose.

Patients will continue on 50mg daily for cycle 4 days 2-7, then 100mg daily on cycle 4 days 8-14, then 200mg daily on cycle 4 days 15-21, and finally 400mg daily on cycle 4 days 22-28. For the initial doses of 100mg, 200mg, and 400mg, TLS labs should be checked prior to initiating the higher dose, approximately 6-8 hours post dose, and approximately 24 hours post dose, with dose escalation occurring only if criteria for TLS are not met.

For the remaining length of therapy, venetoclax will be given at a dose of 400mg daily.

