Corrected calcium ≤7.0 mg/dL (1.75 mmol/L) AND Patient symptomatic (e.g., muscle cramps, hypotension, tetany, cardiac arrhythmias) in the presence of hypocalcemia	 Administer calcium gluconate 50 to 100 mg/kg IV slowly with ECG monitoring. Telemetry. Recheck potassium, phosphorus, uric acid, calcium, and creatinine in 1 hour. If calcium normalized 1 hour later, repeat potassium, phosphorus, uric acid, calcium, and creatinine 2 and 4 hours later, if no other evidence of tumor lysis. Calculate corrected calcium and ionized calcium if albumin is low.
Hyperphosphatemia	
Phosphorus≥5.0 mg/dL (1.615 mmol/L) with ≥0.5 mg/dL (0.16 mmol/L) increase	 Administer a phosphate binder (e.g., aluminum hydroxide, calcium carbonate, sevelamer hydroxide, or lanthanum carbonate). Nephrology notification (dialysis required for phosphorus > 10 mg/dL) Recheck potassium, phosphorus, uric acid, calcium, and creatinine in 1 hour. If phosphorus < 5.0 mg/dL 1 hour later, repeat potassium, phosphorus, uric acid, calcium, and creatinine 2 and 4 hours later, if no other evidence of tumor lysis.
Creatinine	
Increase≥25% from baseline	 Start or increase rate of IV fluids. Recheck potassium, phosphorus, uric acid, calcium, and creatinine in 1 to 2 hours.

IV=intravenous; ULN=upper limit of normal; WNL=within normal limits.

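### Appendix D prints two different phosphorus values as one laboratory-TLS cut-off, and section 5.3 lets 20 mg venetoclax continue where Appendix E part 2 bars it

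*Combined protocol and SAP*

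**What the plan says.** **Phosphorus.** Appendix D Table 1 lists the phosphorus criterion as a value of at least "1.45 mmol/L or 5mg/dL", or a 25% increase from baseline. Laboratory TLS needs two or more elements, and the table note adds: "Either the absolute value or the percent change for each element can count towards one criterion". In Appendix E, the hyperphosphatemia row starts at "5.0 mg/dL (1.615 mmol/L"), with a rise of at least 0.5 mg/dL.

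**Dosing after the first 20 mg.** Section 5.3 (Venetoclax) has low- and medium-risk patients tested at about 6-8 hours and again about "24 hours after the initial dose (prior to the second dose of venetoclax on cycle 4 day 2"). If Cairo-Bishop criteria are met, it refers management to Appendix E and, in the same sentence, says "the patient will either have drug held or continue at 20mg daily (depending on severity) until the changes resolve". Section 5.2, for cycle 4 days 1, 2, 8, 15 and 22, says: "If criteria for TLS are met, the venetoclax dose should be delayed until electrolytes return to baseline". Appendix E part 1 covers the first 24 hours after a first dose or increase and stops dosing when one of its own listed abnormalities is met. Part 2 covers longer intervals and stops dosing whenever laboratory TLS (two or more elements) is present.

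**Use of the definition.** Section 1.3 lists the rate of clinical and laboratory TLS as a secondary objective, and section 13.6 analyses it descriptively.

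**The concern.** One criterion should have one value. If the two units give different cut-offs, the same chemistry can be laboratory TLS when read in mmol/L and not when read in mg/dL. That classification feeds a secondary safety endpoint and, through section 5.2, decides whether a ramp-up dose goes ahead.

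The dosing text raises a separate, more practical problem. A clinician following 5.3 may give 20 mg again to a patient with laboratory TLS, while one following Appendix E part 2 must withhold it. Section 5.3 does not say what severity separates holding from continuing. The protocol reports fatal TLS with venetoclax (sections 2.2.1.12 and 7.1), and section 5.4 places the highest TLS risk of this study in this cycle, so the instruction should be unambiguous.

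**Working it through.** **A. Phosphorus**

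Inputs: the Appendix D and E values above; atomic mass of phosphorus 30.974 g/mol; mmol/L = mg/dL x 10 / 30.974.

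1. Appendix E reproduces: 5.0 mg/dL = 50/30.974 = 1.614 mmol/L (printed 1.615), and 0.5 mg/dL = 5/30.974 = 0.161 (printed 0.16).
2. Appendix D does not: 1.45 x 30.974/10 = 4.49 mg/dL, not 5. Using only Appendix E's own ratio, 1.615/5.0 = 0.323 and 1.45/0.323 = 4.49 mg/dL.
3. Gap: 1.614/1.45 = 1.113, or 11%. In mg/dL the disputed band runs from 4.491 to just under 5.0, a width of 0.509.
4. Two neighbouring rows convert properly: uric acid 8 mg/dL = 476 umol/L, and calcium 7 mg/dL = 1.747 mmol/L (printed 1.75). Rounding does not explain the phosphorus row. (The potassium row has a unit slip of its own, mg/L where Appendix E has mEq/L; it is not part of this point.)
5. When a call changes: a rise of 25% counts by itself, so the absolute value matters only for smaller rises. With no other element met, phosphorus alone is not TLS; with two others met, TLS is already present. So exactly one other element must be met.
6. Share of the band reached by a rise under 25% = (min(1.25 x baseline, 5.0) - 4.491)/0.509, floored at zero:

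| Baseline, mg/dL | Share of band |
|---|---|
| 3.5 | 0% |
| 3.7 | 26% |
| 3.8 | 51% |
| 3.9 | 75% |
| 4.0 or above | 100% |

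These are shares of a numeric interval, not of patients.

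7. Example: phosphorus 4.0 to 4.8 mg/dL is +20% and 48/30.974 = 1.55 mmol/L. With one other element this is laboratory TLS on the mmol/L value and not on the mg/dL value.

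**B. Dosing**

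Take a low-risk patient after the first 20 mg: uric acid 4.0 to 5.0 mg/dL (5.0/4.0 = +25%), phosphorus 3.0 to 3.75 mg/dL (3.75/3.0 = +25%), nothing else changed. Two elements are met, so this is laboratory TLS under Appendix D.

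- *Appendix E part 1:* uric acid is below 8.0, phosphorus is below 5.0, and potassium, calcium and creatinine are unchanged. No trigger is met, so part 1 does not stop dosing.
- *Day 2:* 5.3 allows 20 mg or a hold. Section 5.2 says to delay the dose, but it introduces its listed days as those of initiation or escalation, so the delayed dose may be only the 50 mg step.
- *Day 3, about 48 hours after the first dose:* part 2 applies. If the two abnormalities persist, no dose may be given. Section 5.3 still allows 20 mg daily until they resolve.

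The day 3 instructions cannot both be followed if the clinician takes the option to continue.

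**The case against.** **On phosphorus.** Both appendices give 5 mg/dL, and the sites described in section 2.4 are the lead center and its community affiliates. Nothing shows that the mmol/L figure is ever applied; if every site uses mg/dL, no call changes. That stands, and it limits the consequence. It does not make the two printed values equal.

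**On dosing.** The 5.3 sentence itself points to Appendix E. The notes to Table 6 in section 6.1 require the investigator to review the 24-hour values before the next ramp-up dose, and the text that follows requires about 24 hours of stable electrolytes after aggressive correction. The example above was also chosen to be mild. These points narrow the problem without closing it. The reference to Appendix E and the permission to continue share a sentence, and part 2 forbids what that permission allows. Review before dosing is not a hold, and the stability rule applies only after aggressive correction. Defining severity in 5.3 would not help by itself, because part 2 has no severity exception.

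**Stronger readings that the documents do not support.**
- *That 5.2 plainly withholds 20 mg on day 2.* It can be read as covering only the escalation to 50 mg.
- *That the 100, 200 and 400 mg steps are left open*, because 5.3 speaks only of escalation ("with dose escalation occurring only if criteria for TLS are not met"). Appendix E part 2 covers dose increases and stops any dose during laboratory TLS, and 5.2 names days 8, 15 and 22.
- *That the section 13.4 safety rule is distorted*, since clinical TLS requires laboratory TLS. That rule concerns the first 10 patients to receive a cycle of triple therapy, and cohort 1 has completed enrollment (section 13.2).

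**Conclusion.** Both points hold within limits.

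The Appendix D phosphorus values are 11% apart, and Appendix E's own conversion shows it. Taking 5 mg/dL as intended, because both appendices print it, the mmol/L value is the lower one: applying it over-calls TLS and delays a dose, and does not under-protect. Any changed call rests on the assumption that a site applies the mmol/L value, which the documents do not state, and on the two further conditions in the working.

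The firm dosing conflict is between 5.3 and Appendix E part 2, for low- and medium-risk patients whose laboratory TLS persists more than 24 hours after the first 20 mg. On day 2 the conflict with 5.2 depends on how 5.2 is read, and with Appendix E part 1 it arises only when one of that part's triggers is met.

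The effect on the reported TLS rate cannot be sized: the documents give no phosphorus distribution and no count of patients continued on 20 mg. The primary endpoint and sample size do not depend on any of this.

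**What to change.** 1. Change the phosphorus row of Appendix D Table 1 to 1.615 mmol/L or 5 mg/dL, matching Appendix E. If 1.45 mmol/L was the intended value, change the other unit to 4.5 mg/dL instead.
2. In section 5.3, delete the alternative of continuing 20 mg daily, with its bracket on severity, so that venetoclax is held until the changes resolve and then goes to 50 mg.

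No added sentence is needed for the 100, 200 and 400 mg steps.

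The cost is a text amendment. No new samples are required, and past laboratory-TLS calls can be rechecked from recorded chemistries. The downside is an occasional delay in ramp-up, which 5.3 already accepts: the schedule "cannot be shortened, but may be lengthened if TLS is observed".

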1. FIRST DOSE OF VENETOCLAX OR DOSE INCREASE

- Within the first 24 hours after either the first dose or dose increase, if any laboratory criteria below are met, the patient should be hospitalized for monitoring and the investigator notified. No additional venetoclax doses should be administered until resolution. A rapidly rising serum potassium level is a medical emergency.
- Nephrology (or acute dialysis service) must be consulted/contacted on admission (per institutional standards to ensure emergency dialysis is available).
- IV fluids (e.g., D5 1/2 normal saline) should be initiated at a rate of at least 1 mL/kg/h rounded to the nearest 10 mL (target 150 to 200 mL/h; not < 50 mL/h). Modification of fluid rate should also be considered for individuals with specific medical needs.
- Monitor for symptoms or signs of TLS (e.g., fever, chills, tachycardia, nausea, vomiting, diarrhea, diaphoresis, hypotension, muscle aches, weakness, paresthesias, mental status changes, confusion, and seizures). If any clinical features are observed, recheck potassium, phosphorus, uric acid, calcium, and creatinine within 1 hour.
- Vital signs should be taken at time of all blood draws or any intervention.
- The management recommendations below focus on the minimum initial responses required. If a diagnosis of TLS is established, ongoing intensive monitoring and multi-disciplinary management will be per institutional protocols.

Recommendations for Initial Management of Electrolyte Abnormalities and Prevention of Tumor Lysis Syndrome (TLS)

Abnormality	Management Recommendations
Hyperkalemia (including	rapidly rising potassium)
Potassium ≥ 0.5 mmol/L increase from prior value (even if potassium within normal limits [WNL])	 Recheck potassium, phosphorus, uric acid, calcium, and creatinine in 1 hour. If further≥0.2 mmol/L increase in potassium, but still<up>er limit of normal (ULN), manage per potassium≥ULN. Otherwise recheck in 1 hour.</up> Resume per protocol testing if change in potassium is<0.2 mmol/L, and potassium<uln, and="" evidence="" li="" lysis.<="" no="" of="" other="" tumor=""> At discretion of investigator, may recheck prior to hospitalization. If stable or decreased, and still WNL, hospitalization is at the discretion of the investigator. Potassium, phosphorus, uric acid, calcium, and creatinine must be rechecked within 24 hours. </uln,>
Potassium > upper limit of normal	 Perform immediate ECG and commence telemetry. Nephrology notification with consideration of initiating dialysis Administer Kayexalate 60 g (or Resonium A 60 g). Administer furosemide 20 mg IV × 1. Administer calcium gluconate 100 to 200 mg/kg IV slowly if there is ECG/telemetry evidence of life-threatening arrhythmias. Recheck potassium, phosphorus, uric acid, calcium, and creatinine in 1 hour. If potassium < ULN 1 hour later, repeat potassium, phosphorus, uric acid, calcium, and creatinine 1, 2, and 4 hours later, if no other evidence of tumor lysis.
Potassium≥6.0 mmol/L (6.0 mEq/L) and/or symptomatic (e.g., muscle cramps, weakness, paresthesias, nausea, vomiting, diarrhea)	 Perform immediate ECG and commence telemetry. Nephrology assessment with consideration of initiating dialysis Administer Kayexalate 60 g (or Resonium A 60 g). Administer furosemide 20 mg IV×1. Administer insulin 0.1 U/kg IV+D25 2 mL/kg IV. Administer sodium bicarbonate 1 to 2 mEq/kg IV push. If sodium bicarbonate is used, rasburicase should not be used as this may exacerbate calcium phosphate precipitation. Administer calcium gluconate 100 to 200 mg/kg IV slowly if there is ECG/telemetry evidence of life-threatening arrhythmias. Do not administer in same IV line as sodium bicarbonate. Recheck potassium, phosphorus, uric acid, calcium, and creatinine every hour.

Abnormality	Management Recommendations
Hyperuricemia	
Uric acid≥8.0 mg/dL (476 μmol/L)	 Consider rasburicase (dose per institutional guidelines). If rasburicase is used, sodium bicarbonate should not be used as this may exacerbate calcium phosphate precipitation. Recheck potassium, phosphorus, uric acid, calcium, and creatinine in 1 hour.
Uric acid ≥ 10 mg/dL (595 µmol/L) OR Uric acid ≥ 8.0 mg/dL (476 µmol/L) with 25% increase and creatinine increase ≥ 0.3 mg/dL (≥ 0.027 mmol/L) from predose level	 Administer rasburicase (dose per institutional guidelines). If rasburicase is used, sodium bicarbonate should not be used as this may exacerbate calcium phosphate precipitation. Consult nephrology. Recheck potassium, phosphorus, uric acid, calcium and creatinine in 1 hour. If uric acid < 8.0 mg/dL 1 hour later, repeat potassium, phosphorus, uric acid, calcium, and creatinine 2 and 4 hours later, if no other evidence of tumor lysis.
Hypocalcemia	
Corrected calcium ≤7.0 mg/dL (1.75 mmol/L) AND Patient symptomatic (e.g., muscle cramps, hypotension, tetany, cardiac arrhythmias) in the presence of hypocalcemia	 Administer calcium gluconate 50 to 100 mg/kg IV slowly with ECG monitoring. Telemetry. Recheck potassium, phosphorus, uric acid, calcium, and creatinine in 1 hour. If calcium normalized 1 hour later, repeat potassium, phosphorus, uric acid, calcium, and creatinine 2 and 4 hours later, if no other evidence of tumor lysis. Calculate corrected calcium and ionized calcium if albumin is low.
Hyperphosphatemia	
Phosphorus≥5.0 mg/dL (1.615 mmol/L) with ≥0.5 mg/dL (0.16 mmol/L) increase	 Administer a phosphate binder (e.g., aluminum hydroxide, calcium carbonate, sevelamer hydroxide, or lanthanum carbonate). Nephrology notification (dialysis required for phosphorus > 10 mg/dL) Recheck potassium, phosphorus, uric acid, calcium, and creatinine in 1 hour. If phosphorus < 5.0 mg/dL 1 hour later, repeat potassium, phosphorus, uric acid, calcium, and creatinine 2 and 4 hours later, if no other evidence of tumor lysis.
Creatinine	
Increase≥25% from baseline	 Start or increase rate of IV fluids. Recheck potassium, phosphorus, uric acid, calcium, and creatinine in 1 to 2 hours.

IV=intravenous; ULN=upper limit of normal; WNL=within normal limits.

